10.4 Statistical considerations

The sample size calculation has been performed based on overall survival data. This is the primary endpoint and therefore no calculation has been performed based on changes in QL. The primary QL endpoints that are considered relevant to this trial are global QOL. The QOL data will inform the hypothesis that we expect no differences between arms using the global QOL scale during treatment, but there may be a later benefit to the adjuvant therapy arm if disease progression is achieved, thereby leading to a better global QOL. Hence, the global quality of life scale of the QLQ-C30 will be used as the primary QL outcome of interest. Based on the work of Osoba et al. (Ref. 27), a difference of 10 points on a 100 point scale between the two treatment arms will be considered as clinically significant. The standard deviation of the global QoL scale is approximately 20 points. With a minimal effect size of 0.5 (i.e. one-half standard deviation), with alpha set at 0.5 and beta at 0.20 (power 0.80), a minimum of 64 patients per treatment arm is required. The other scales of fatigue and social functioning will be analyzed as secondary QOL endpoints. The remaining scales will only be analyzed on an exploratory basis. Data will be scored according to the algorithm described in the EORTC QLQ-C30 scoring manual. All scales and single items are scored on categorical scales and linearly transformed to 0-100 scales where:

A high score for a symptom scale or item represents a high level of symptoms or problems.

A high score for a functional scale represents a high or healthy level of functioning.

A high score for the global health status/QoL represents high QoL.

When performing a QoL analyses complications may arise due to large quantities of missing data. This issue has a bearing on whether a valid comparison of the treatment arms is being made.

In QoL research there are two main types of missing data: (1) item non-response, (2) unit non-response (the whole questionnaire is missing for a patient.) As item non-response occurs less than 2% on average in the QLQ-C30 it is not such a major problem and thus the methods described in the EORTC QLQ-C30 scoring manual for handling item non-response will be used. For missing questionnaires, it is necessary to identify both the extent of missing questionnaires and the main process of missing data. Three different types of missing data processes may exist: missing completely at random (MCAR), missing at random (MAR), and missing not at random (MNAR, informative dropout mechanism). These have distinct consequences for data analysis.

If the missing data process is considered to be non-ignorable (MNAR) then the quality of life will be compared between groups using longitudinal data modeling techniques (i.e. Proc mixed in SAS with either selection models or pattern-mixture models) in combination with a logistic regression for the dropout process.

If the missing data mechanism can be considered ignorable (MAR), then standard longitudinal data analysis will be used (PROC mixed in SAS).

If the data are MCAR then complete case analysis can be used without biasing the results.

Statistical tests will be performed using a two-sided significance level of 5%.

For all quality of life domains and items, cross-sectional descriptions of the average scores will be presented by treatment arm at each time point of assessment together with confidence intervals and a graphical display of the patterns of change over time will be provided.

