Objective(s)	
This trial is a follow up study of EORTC 26981 and of EORTC 26951 addressing the overall strategy of optimizing the treatment in newly diagnosed anaplastic glioma patients without combined 1p/19q loss. Patients will be randomized immediately after surgery to one of the four following therapeutic options:
 
Arm 1 : RT alone (and further treatment including chemotherapy at progression) Arm 2 : RT & concurrent CT Arm 3 : RT + adjuvant CT Arm 4 : RT & concurrent CT + adjuvant CT
 
Twelve months of adjuvant treatment is foreseen. Patients will be included based on the 1p/19q status of the tumor. Centers with known expertise in 1p/19q testing will be allowed to include patients based on local testing, with central review for 1p/19q testing (and histology). For sites without access to 1p/19q testing a central facility will be created. Methylation status of the MGMT promoter gene will be a stratification factor.
 
Primary objectives:
 
To assess whether concurrent radiotherapy with daily temozolomide chemotherapy improves overall survival as compared to no daily temozolomide in non-1p/19q deleted anaplastic glioma.
 
To assess whether adjuvant temozolomide chemotherapy improves survival as compared to no adjuvant temozolomide chemotherapy in non-1p/19q deleted anaplastic glioma

Methodology	Phase III – difference
Number of patients Number planned (Statistical design) Number analyzed	
This is a 2 by 2 factorial design with Overall Survival as the primary endpoint when comparing:
 
Patients receiving RT alone or RT + adjuvant TMZ to those receiving RT & concurrent TMZ or RT & concurrent TMZ + adjuvant TMZ.
 
[Comparison I]: test for superiority of the concurrent TMZ chemotherapy]
 
Patients receiving RT alone and RT & concurrent TMZ to those receiving RT + adjuvant TMZ or RT & concurrent TMZ + adjuvant TMZ.
 
[Comparison II]: test for superiority of the adjuvant TMZ chemotherapy]
 
For both comparisons, to detect a reduction of the risk of death of 22.5% based on a two-sided logrank test, at an overall significance level of 5% and a power of 83%, a total of 534 events are needed. With an estimated accrual rate of 150 patients per year, a total of 748 patients can be recruited in 5 years. A minimum follow-up of 2 ½ years will be needed to

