8.1 Statistical design

8.1.1 Sample size

This is a 2 by 2 factorial design with Overall Survival as the primary endpoint when comparing:

- Patients receiving RT alone or RT + adjuvant TMZ to those receiving RT & concurrent TMZ or RT & concurrent TMZ + adjuvant TMZ.

[Question I: test for superiority of the concurrent TMZ chemotherapy]

- Patients receiving RT alone and RT & concurrent TMZ to those receiving RT + adjuvant TMZ or RT & concurrent TMZ + adjuvant TMZ.

[Question II: test for superiority of the adjuvant TMZ chemotherapy]

The hypotheses are the following:

- In the EORTC trial 26951 for Anaplastic Oligodendroglioma and Oligoastrocytoma tumors, patients with no combined 1p/19q LOH treated by RT alone had a median survival of 24 months. In the EORTC trial 26882 for Anaplastic Astrocytoma, patients treated by RT alone had a median survival of 24 months.
- No interaction is anticipated between the concurrent and adjuvant temozolomide treatment that are assumed to contribute equally to the survival improvement.
- In the EORTC trial 26981, comparing RT & Concurrent TMZ + adjuvant to RT alone, the estimated Hazard Ratio was 0.63 and its 95% Confidence Interval [0.52-0.75].

The following table summarizes the statistical parameters of the design. A Hazard Ratio (HR) of 0.775 is assumed for both questions.

RT		No adjuv CT (median OS)	Adjuv CT (median OS)	Question I	
				Median OS	HR
No conc CT		24 m	31 m	(24+31)/2=27.5	0.775
Conc CT		31 m	40 m	(31+40)/2=35.5	
Question II	Median OS	27.5	35.5		
	HR	0.775			

For both questions, to detect a reduction of the risk of death of 22.5%, based on a two-sided logrank test, at an overall significance level of 5% and a power of 83%, a total of 534 events are needed. With an estimated accrual rate of 150 patients per year, a total of **748** patients should be recruited within approximately 5 years. A minimum follow-up of 2 ½ years will be needed to observe the required number of events. One interim analysis for efficacy is planned when 41% of the events have been observed (219). To perform this interim look, 11 additional events are necessary. Power of the trial was slightly increased in order to compensate for the loss of information due to patients dropping out before starting the adjuvant treatment. It is estimated that 10% of the patients will fail during or within the month following radiotherapy.

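### The QoL method is picked by a missing-data verdict that observed data cannot settle: fix one mixed model, drop complete case, and always run an MNAR sensitivity analysis

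*Combined protocol and SAP*

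**What the plan says.** Section 10.4 of the combined protocol and SAP makes the global scale of the QLQ-C30 the primary QoL outcome, and Section 10.1 treats QoL as an important secondary endpoint. For whole missing questionnaires, Section 10.4 first asks for the extent and main process of missingness to be identified. The method then follows from the answer:

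- **MNAR:** "If the missing data process is considered to be non-ignorable (MNAR) then the quality of life will be compared between groups" by selection or pattern-mixture models, combined with a logistic model for dropout.
- **MAR:** a standard longitudinal analysis in PROC MIXED.
- **MCAR:** "If the data are MCAR then complete case analysis can be used without biasing the results".

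The section gives no test, criterion, timing or decision-maker for the verdict. It names no default model and no sensitivity analysis to run beside the chosen one.

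The benchmark for relevance is in the same section: "a difference of 10 points on a 100 point scale between the two treatment arms will be considered as clinically significant".

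**The concern.** A rule of this kind works only if its input can be known. Observed data can give evidence against MCAR, but failing to find such evidence does not establish MCAR. MAR and MNAR differ only in how missingness depends on values nobody saw, so no analysis of the collected forms can tell them apart. The analyst would choose among three methods, which can give different answers, after seeing the data and without a stated criterion. MNAR models would run only if someone declared the data MNAR.

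The documents also make MCAR doubtful:

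- Section 1.1.3 says that many glioma patients worsen at progression.
- Section 10.4 warns that a lot of data may be missing and that this bears on the validity of the comparison.
- Section 10.5 expects worse baseline scores to go with poorer survival.
- Section 10.3.1 collects forms until death, and the design plans for many deaths.

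At stake is the credibility of the between-arm QoL comparison, above all the adjuvant comparison that Section 10.1 names as the main QoL objective.

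**Working it through.** **1. The plan's own figure.** Inputs from Section 10.4: difference 10 points; "The standard deviation of the global QoL scale is approximately 20 points"; power 0.80. With n = 2(z₁₋α/₂ + z₁₋β)²(SD/δ)² and two-sided α = 0.05:

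n = 2 × (1.960 + 0.842)² × (20/10)² = 62.8, so 63; the t-test version gives 63.77, so 64.

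The plan's 64 is reproduced. The printed text reads "with alpha set at 0.5 and beta at 0.20 (power 0.80), a minimum of 64 patients per treatment arm is required"; with α = 0.5 two-sided the same formula gives 2 × (0.674 + 0.842)² × 4 = 18.4, so 19. The printed 0.5 is therefore read as a misprint, since later in the section "Statistical tests will be performed using a two-sided significance level of 5" per cent.

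**2. Precision is not the problem.** The protocol summary says "a total of 748 patients can be recruited in 5 years". Assuming equal allocation, that is 748/2 = 374 per side of each factorial question. At 50% of forms (187 per side) the standard error is 20 × √(2/187) = 2.07, and 10/2.07 = 4.8, so power for 10 points exceeds 99%. Bias matters more here.

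**3. How much does the choice of method matter?** The documents give no figure, so this was simulated.

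- From the documents: 374 per side, SD 20, and 70% retention at the last visit (the action level in Section 10.3.2).
- Assumed: baseline plus 4 visits, exchangeable correlation 0.5 or 0.7, monotone dropout, a second retention level of 50%, and dropout log-odds per SD of QoL of −1 in both arms, or −1.5 in one and −0.5 in the other. True difference was 0 or 10.
- 1,000 runs per scenario. Standard errors of about 1.5 to 2.1 points give a Monte Carlo error of about 2.1/√1000 = 0.07 at most.

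Bias in the last-visit difference, in points:

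| Mechanism | Dependence on QoL | Complete case | Mixed model, all forms |
|---|---|---|---|
| MCAR | none | at most 0.09 | at most 0.09 |
| MAR | equal, true difference 0 | about 0 | about 0 |
| MAR | equal, true difference 10 | −0.5 to −0.9 | within 0.15 |
| MAR | differs by arm | 2.5 to 5.7 in size | at most about 0.1 |
| MNAR | equal, true difference 10 | −1.1 to −1.6 | −0.4 to −0.8 |
| MNAR | differs by arm | 3.0 to 7.0 in size | 1.2 to 4.2 in size |

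The sign depends on which arm has the stronger dependence. Under MCAR the mixed model's variance was 0.67 to 0.91 of that of complete case. Under MAR it was at times up to 1.14 times the complete-case variance, but there the complete-case estimate is generally the biased one.

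**4. One scenario in full.** Correlation 0.5, 50% retention, no true difference, slopes −1.5 and −0.5. Under MAR, complete case gives −4.29 (SE 1.93) and the mixed model +0.02 (SE 2.03). The error is 4.29/10 = 43% of the relevance threshold. Under MNAR, complete case gives −5.96 and the mixed model −3.78, so 3.78/5.96 = 63% of the bias remains.

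**5. Death.** Section 8.1.1 plans the trial "at an overall significance level of 5% and a power of 83%, a total of 534 events are needed". That is 534/748 = 71% of patients whose QoL series would end in death by the final analysis. A likelihood mixed model treats scores after death as merely missing, and Section 10.4 does not say whether that is intended.

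**The case against.** The complete-case sentence is conditional, permissive and correct: under MCAR that analysis is unbiased. Nothing says the data are MCAR or that complete case will be used. If dropout depends on past scores, the plan already prescribes PROC MIXED. The 2.5 to 5.7 points are thus the cost of a misclassification whose frequency is unknown. It may be rare: in a similar simulated setting (350 per group, 4 visits, correlation 0.6, log-odds −0.3 to −1.0 per SD, all assumed), a logistic regression of dropout on the last score rejected MCAR in 99 to 100% of trials. Section 10.3.2 also compares compliance between arms at each time point and sets a 70% action level. It attributes missing forms chiefly to centres not collecting them on time, and forms are still required after progression.

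Much of this stands. The figures illustrate misclassification and do not predict this trial's result. But the plan names no MCAR test, so detection is not assured, and a compliance difference between arms does not identify the mechanism. None of it helps separate MAR from MNAR, and none of it gives complete case an advantage.

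A reader might also infer that one mixed model cures the problem at no cost. It does not: it leaves 1.2 to 4.2 points of bias when MNAR dropout differs by arm, it does not settle the handling of death, and it moves the MNAR models from possible primary analyses to sensitivity analyses.

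**Conclusion.** The point holds as a cheap improvement to a secondary endpoint. Section 10.4 sets a selection rule whose input cannot be established from the data, so the primary QoL comparison is not fixed in advance. The complete-case option is dominated: it has no advantage under MCAR, and it could be off by a quarter to over half of the 10-point threshold if MAR data were misjudged as MCAR and dropout dependence differed by arm. This size rests on the assumed correlation, visit pattern and dropout slopes.

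A reader might infer that complete-case analysis is biased in this trial. The documents do not support that. They make MCAR doubtful, but they report no dropout pattern, and the bias is near zero when dependence is equal in both arms and the arms do not differ. The overall survival analysis is not touched.

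**What to change.** In Section 10.4, delete the complete-case branch and the choice of method by mechanism. Replace them with wording such as:

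> The primary analysis of global QoL is a linear mixed model (PROC MIXED) on all available forms, with baseline score, visit, question and question-by-visit. A pattern-mixture or selection model is run as an MNAR sensitivity analysis whatever is concluded about the missing-data mechanism.

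The text should also state:

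- the main contrast (Section 10.1 points to the adjuvant question), the covariance structure and the time points; Section 10.3.1 has three-monthly forms that Section 6.4.1 does not, and these need reconciling;
- whether the target is QoL while alive or, if not, how death is handled, because the mixed model does not settle this by itself;
- 0.05 in place of the printed 0.5 for alpha.

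Section 8.3.2 records a recommendation to release results on all endpoints for the adjuvant comparison. The documents do not say whether QoL has been analysed. If it has, the choice made should be documented; if not, the model should be fixed first.

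The cost is SAP wording and slightly more analysis work, using methods the plan already names. No new patients or data are needed. The downside is that MNAR models become sensitivity analyses only, while the primary model stays biased if dropout is MNAR and differs by arm.

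### Section 10.4 expects no difference in global QoL during treatment but plans only a 5% test of difference, with no between-arm confidence interval and no link to its 10-point threshold

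*Combined protocol and SAP*

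**What the plan says.** Section 10.4 gives a two-part hypothesis: "we expect no differences between arms using the global QOL scale during treatment, but there may be a later benefit to the adjuvant therapy arm". Section 10.1 says the same. The outcome is named: "the global quality of life scale of the QLQ-C30 will be used as the primary QL outcome of interest". The section also states what counts as relevant: "a difference of 10 points on a 100 point scale between the two treatment arms will be considered as clinically significant". For sizing it adds "The standard deviation of the global QoL scale is approximately 20 points", prints the error rates as "with alpha set at 0.5 and beta at 0.20 (power 0.80", and arrives at a minimum of 64 patients per arm.

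The analysis is a longitudinal mixed model, with selection or pattern-mixture variants if dropout is judged informative and complete cases if data are missing completely at random. The one decision rule is "Statistical tests will be performed using a two-sided significance level of 5" per cent. Average scores by arm and time point will be shown with confidence intervals. The section does not mention an interval for the difference between arms, an equivalence or non-inferiority margin, or a rule for concluding that the arms do not differ.

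**The concern.** The on-treatment half of the hypothesis is an expectation of no difference, and the only tool offered for it is a test of difference. Such a test can go wrong in two ways here. With few questionnaires, p above 0.05 may be read as agreement with the expectation although a relevant difference has not been excluded. With many questionnaires, p below 0.05 may be read as contradicting the expectation although the difference is well under the protocol's own 10 points.

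The second case is plausible on the protocol's own terms. Section 10.1 anticipates slightly more fatigue and slightly lower social functioning with adjuvant chemotherapy, so a small real deficit in global QoL would be no surprise. Section 10.1 calls QoL an important secondary endpoint. At stake is whether its on-treatment conclusion follows from the size of the difference or from the number of forms returned.

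**Working it through.** **Inputs.** SD 20, relevant difference 10, power 80%, minimum 64 per arm, two-sided 5% (section 10.4); 748 randomized (section 8.1.1); 70% compliance as the level that triggers action (section 10.3.2). Assumptions: equal allocation, so 748/2 = 374 per side of the adjuvant question and 0.70 × 374 = 262 at the compliance trigger; one comparison of two independent means with SD 20. A repeated-measures model would change the precision somewhat.

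**The plan's own figure.** The normal approximation, 2 × (1.96 + 0.84)² × (20/10)², gives 63 per arm. The two-sample t-test gives 63.8, rounded up to 64. So 64 reproduces as the size for a two-sided test of difference at alpha 0.05. The printed alpha of 0.5 would give only 18 to 19 and looks like a misprint.

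**What each result of the test implies.** The standard error is SE = 20 × √(2/n). The smallest significant observed difference is h = t × SE, where t is the two-sided 5% critical value. If the result is non-significant, the observed difference is below h, so its 95% CI lies inside ±2h. Power at a true difference d is approximately Φ(d/SE − 1.96).

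| n per side | SE | h | bound on CI if non-significant (2h) | P(significant), true 5 points | P(significant), true 3 points |
|---|---|---|---|---|---|
| 64 | 3.54 | 7.0 | 14.0 | 29% | 13% |
| 262 | 1.75 | 3.4 | 6.9 | 82% | 40% |
| 374 | 1.46 | 2.9 | 5.7 | 93% | 54% |

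**At 64 per arm.** Power at a true 10 points is 80.1% by the t-test and 80.7% by the normal approximation. A relevant difference is therefore non-significant in 19% to 20% of trials.

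**Where that risk ends.** 2h falls below 10 from 125 per group with SD 20, or from 194 with an assumed SD of 25. Both are below 262. If single arms were compared (748/4 = 187), 2h is 8.1, so 10 points is still excluded.

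**The alternative rule.** Conclude that there is no clinically relevant difference only if the 95% CI lies within −10 to +10. With a true difference of zero, 80% power needs 86 per arm. Power is about 60% at 64 and above 99% at 262 and 374. The planned size is ample for this rule.

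**The case against.** The strongest reply is that the planned size protects the conclusion. The figure of 64 is a minimum, and at 262 or 374 per side every non-significant result excludes 10 points. That stands. A reader might infer that a non-significant test can never support the expectation; on the plan's SD and numbers that is true only at low form counts, below about 125 per group. The protection is a by-product, though: section 10.4 does not plan the interval that would show it.

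Second, section 10.4 states the 10-point threshold as a general criterion of clinical significance. A reader might infer that it serves only the sample size, and the text does not support that. An analyst following it could decline to call a significant 3-point difference clinically significant. This tempers the second risk, but nothing ties the threshold to the test or to the conclusion.

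Third, a reader might infer that the trial intends to claim that temozolomide leaves QoL unharmed. The documents do not say so. Section 10.1 sets out to determine the impact of adjuvant therapy, the no-difference statement is an expectation that the data will inform, and the protocol summary labels the methodology as a difference design. The later-benefit half of the hypothesis suits a superiority test.

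Fourth, the remedy involves choices. A 90% interval, a one-sided non-inferiority rule or a smaller margin could also be defended. Ten points is lenient: at 262 per side an observed difference of up to about 10 − 3.4 = 6.6 points would still pass, although it is clearly significant. That is a reason to report the estimate every time, not a reason to rely on the p-value.

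**Conclusion.** The mismatch is real but limited. Section 10.4 has no rule that fits its on-treatment expectation, plans no confidence interval for the between-arm difference, and does not connect its 10-point threshold to the conclusion.

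The false reading of no difference matters near the stated minimum of 64 per arm. At the planned size the main error is the opposite one: differences of roughly a third of the relevant size are significant. These figures rest on SD 20, an equal split and a single cross-sectional comparison; the 262 also assumes 70% compliance. The point concerns a secondary endpoint. It does not affect the survival comparisons, and it does not show that the trial is too small for the QoL question.

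**What to change.** In section 10.4, add for the on-treatment hypothesis: estimate the between-arm mean difference in global QoL over the treatment period from the longitudinal model already planned, and report it with its 95% CI. Conclude that there is no clinically relevant difference only if that interval excludes 10 points in both directions. Do not base the conclusion on whether p is above or below 0.05. Give the estimate and interval whatever the result, so that a smaller but significant deficit stays visible. Keep the superiority test for later benefit, also with the CI of the difference. Correct the printed alpha if 0.05 was meant.

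This needs a few sentences and no new patients or forms. It has three small costs:

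- The treatment period must be defined for arms without adjuvant therapy, and the QoL timing reconciled, since section 10.3.1 has three-monthly forms and section 6.4.1 six-monthly ones.
- The leniency of the 10-point margin should be acknowledged, or a smaller one justified. An assumed 5-point margin would have 85% power at 374 per side and 63% at 262.
- Appendix M states that enrolment and treatment are complete, so the rule should be dated and described as added afterwards. Section 8.3.2 records advice to release the adjuvant results on all endpoints; the documents do not say whether QoL was already analysed. If it was, the rule should be presented as post hoc for that comparison.
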